4.1.2.5 Endpoints assessed by Investigators based on CT

In addition to the primary and secondary efficacy endpoints described above, the same set of endpoints (ORR, DoR, CRR, PFS and TTR) assessed by investigators based on CT imaging will also be regarded as secondary endpoints.

For Investigators based endpoints, the date of assessment will be derived following similar rule as in Independent Review Charter session 10.1.

If an assessment may include several methods of evaluation performed over a period of several days within a window of time around an expected assessment date, the date of assessment will be recorded as the date of the last radiographic included in the series for that assessment.

The CT date of progression is defined as the radiographic assessment date of the first time point with overall response as PD for that assessment.

The CT date of first response is defined as the radiographic assessment date when the criteria for CR or PR were first met.

Statistical Analysis Plan of PTCL (Version 3.0)

Protocol Code: DZ2019J0005 (Part B)

Date: Mar 25, 2023

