6.9.1 CT imaging for tumor assessment

All patients will be asked to conduct CT scans (with contrast unless contraindicated) of the neck, chest, abdomen, and pelvis and any other disease sites based on the signs and symptoms as well as bone marrow aspiration/biopsy at screening (within 4 weeks prior to first dosing of AZD4205, bone marrow aspiration/biopsy within 60 days prior to the first dose of AZD4205 is acceptable) for baseline tumor burden assessment.

During treatment, CT scans of the same sites as screening will be done for tumor response assessment within 7 days of Day 1 of Cycle 3, 6, 9 and then every 3 cycles until PD or withdrawal from the study. Any other sites at which new disease is suspected should also be appropriately imaged. Any patient who discontinues study treatment for reasons other than disease progression should have response assessment performed as scheduled in the protocol until disease progression, or death occurs, unless consent is withdrawn. Images for tumor assessment post new anti-cancer therapy will not be collected.

A bone marrow aspiration or biopsy is required to confirm a complete response for patients with bone marrow involvement at baseline.

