4. ENDPOINTS DEFINITION AND DERIVATION

4.1 Efficacy Endpoints

The efficacy endpoints based on the tumor assessments will be assessed according to the Lugano Classification for non-Hodgkin lymphoma (see Session 6.9 and Appendix VI of the CSP for details). The overall response for each participant may be provided from sources as illustrated below:

- For IRC-assessed efficacy endpoints: Final IRC-reported participant level overall response including Best Response, Date of Progression (if applicable), and Date of First Response (if applicable)
- For investigators-assessed efficacy endpoints: Investigator (local radiology) overall responses at each assessment/time point. Participant overall response date will be derived by program (see details in Section 4.1.2.5).

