4.1.2.3 PFS assessed by IRC based on CT

PFS is defined as the time from the date of first dosing until the date of objective disease progression as defined by Lugano classification or death (by any cause) regardless of whether the participant discontinues the study treatments. Progression is identified based on CT imaging evaluated by IRC. Participants who have not progressed or died at the time of analysis will be censored at the time of the latest date of assessment from their last evaluable tumor response assessment. More censoring rules for PFS are presented in Table 1. Symptomatic deterioration will not be regarded as a progression event.

The PFS will be calculated as:

$$\text{PFS (months)} = (\text{date of event/censoring} - \text{first dose date of AZD4205} + 1) / 30.4375.$$

Table 1 Censoring Scheme for PFS

No.	Situation	Date of Progression or Censoring	Outcome
1	No baseline or any post-baseline tumor assessments and without death within two visits (112 days from date of first dose)	Date of first dose	Censored

Statistical Analysis Plan of PTCL (Version 3.0)

Protocol Code: DZ2019J0005 (Part B)

Date: Mar 25, 2023

No.	Situation	Date of Progression or Censoring	Outcome
2	No baseline or any post-baseline tumor assessments and died within two visits (112 days from date of first dose)	Date of death	Event
3	Progression documented between scheduled visits	Date of first radiological PD	Event
4	No progression at the time of data cut-off/discontinuation from the study	Date of last visit with *adequate radiological tumor assessment prior to data cut-off or discontinuation from the study.	Censored
5	Treatment discontinuation for reason other than radiological PD	Data after discontinuation of treatment will be included when determining the time to progression	Event / Censored
6	New anticancer treatment started	Date of last adequate radiological tumor assessment with documented non-progression before start of new treatment	Censored
7	Death before first PD assessment	Date of death	Event
8	Death between scheduled tumor assessment visits	Date of death	Event
9	Death or progression after more than one missed visit (CT scans will be done for tumor assessments within 7 days of Day 1 of Cycle 3, 6, 9 and then every 3 cycles thereafter until PD)	Date of last adequate radiological tumor assessment with documented non-progression	Censored

* Adequate tumor assessment is a radiologic assessment of CR, PR, SD, non-CR/non-PD or PD as determined by investigators.

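### For investigator-assessed endpoints, SAP 4.1.2.5 dates a multi-day assessment at its last radiograph, so progression already shown by an earlier scan in the series is dated late and investigator PFS is lengthened by that gap

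*SAP*

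**What the plan says.** SAP 4.1.2.5 covers the secondary endpoints assessed by investigators on CT. It introduces its dating rule as follows: "For Investigators based endpoints, the date of assessment will be derived following similar rule as in Independent Review Charter session 10.1". For an assessment that uses several methods over several days around an expected date, "the date of assessment will be recorded as the date of the last radiographic included in the series for that assessment".

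Two event dates are built on that assessment date:

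- Progression: "The CT date of progression is defined as the radiographic assessment date of the first time point with overall response as PD for that assessment".
- Response: "The CT date of first response is defined as the radiographic assessment date when the criteria for CR or PR were first met".

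No separate rule selects the earliest scan for progression.

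SAP 4.1.2.3, Table 1, row 3 deals with progression found between scheduled visits and assigns "Date of first radiological PD". No row of that table dates ordinary progression found at a scheduled visit.

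Protocol 6.9.1 schedules on-treatment CT "within 7 days of Day 1 of Cycle 3, 6, 9" and every three cycles after that.

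IRC dates have a different source. SAP 4.1 takes the progression and first-response dates from the IRC's final participant-level report and does not derive them under 4.1.2.5.

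**The concern.** The same date serves two events that need different evidence. For CR or PR, all site categories in Protocol Appendix VI, Table 14 have to be checked, so the last scan is a reasonable date for response. Progression under the same table needs only one of several criteria, such as one lesion that has grown enough or one new site. A scan early in the series can therefore settle progression before the series is complete.

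When that happens, the stated rule moves the investigator PFS event later, and it can never move it earlier. The size depends on how each site spreads its scans over days, which has nothing to do with the drug. SAP 5.5.3 plans no sensitivity analysis, so the effect would not be examined elsewhere. Part B is meant to support a marketing application, and Protocol 6.9.4.2 plans a comparison of independent and investigator assessments. The dating convention should therefore be explicit and the same on both sides.

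**Working it through.** **The plan's own figure.** The documents give no figure for PFS or for the dating rule. The only design figure is the ORR power in SAP 2.4: N = 100, null ORR 15%, assumed ORR 27%, two-sided 5%, exact binomial, 84.5%. The smallest count r with P(X ≥ r | 0.15) ≤ 0.025 is 23, where the one-sided tail is 0.0221. P(X ≥ 23 | 0.27) = 0.8448, so the stated power reproduces. The exact 95% interval for 27/100 is 18.6% to 36.8%, also as stated. Neither figure depends on which scan in a series dates PD.

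**Which date the rule gives.** The investigator progression date is the assessment date of the first time point called PD. If that assessment spans several days, its date is that of the last radiograph. Together these make PD date = last radiograph in the series.

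**Size of the delay.**

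- Delay = date of last radiograph − date of the earliest radiograph meeting a PD criterion.
- It is 0 if all scans are on one day, or if PD is first met on the last scan.
- Day 1 of cycle c is study day 21(c − 1) + 1, which gives days 43, 106 and 169 for Cycles 3, 6 and 9. Reading the window as ±7 days, scans fall on days 36–50, 99–113 and 162–176. The longest possible span is 14 days.
- The SAP's conversion is PFS (months) = (event date − first dose date + 1)/30.4375, so a delay of d days adds d/30.4375 months.

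For scale only, the last column compares this with the 3 to 4 months of PFS that Protocol 2.1 cites for existing treatment, which is not this trial's PFS.

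| Delay (days) | Months added | Share of 4 to 3 months |
|---|---|---|
| 1 | 0.03 | 0.8% to 1.1% |
| 3 | 0.10 | 2.5% to 3.3% |
| 7 | 0.23 | 5.7% to 7.7% |
| 14 | 0.46 | 11.5% to 15.3% |

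**Illustration (invented dates).** A chest CT on study day 99 shows a new lesion that meets PD, and an abdominal MRI follows on day 102. The present rule gives 102/30.4375 = 3.35 months. Dating at the first qualifying scan gives 99/30.4375 = 3.25 months. The difference is 3/30.4375 = 0.10 months.

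**Average over all PD events.** The share affected is not in the documents, so 10% to 100% is assumed. Mean shift = share × d/30.4375.

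- 1-day delay: 0.10 × 0.033 = 0.003 to 1.00 × 0.033 = 0.03 months.
- 14-day delay: 0.10 × 0.460 = 0.05 to 1.00 × 0.460 = 0.46 months.

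**Duration of response.** Investigator DoR changes only by the net of the shifts in its start and end dates. If the response date stays at the last scan and only the PD date moves, DoR shortens by the PD gap in responders who later progress.

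**The case against.** The strongest reply is that one date per assessment is a coherent, pre-specified convention. PFS is a secondary endpoint, described by Kaplan-Meier estimates with no test and no comparator arm (SAP 5.5.2.2). After Cycle 3, scans are three cycles (63 days) apart, which blurs PFS more than a few days within one assessment. Nothing shows that multi-day series are common: CT of all sites is the standard assessment, and Protocol 6.9.2 limits MRI to stated exceptions. All of this stands and keeps the point small. It does not remove the one-way direction of the error, and the SAP itself provides for assessments spread over several days.

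A reader might infer more than the documents support:

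- **That IRC PFS is lengthened too.** The rule is limited to investigator endpoints. The SAP calls it similar to a charter section that is not supplied, so the IRC convention is something to check and not a shown error.
- **That the rule contradicts Table 1.** Row 3 covers only progression between visits and does not say which scan within a series sets the date. It can be read as the first PD time point, which agrees with 4.1.2.5. It is ambiguous rather than contradictory. It also sits in the IRC section and reaches investigator PFS only through the shared analysis method in SAP 5.5.2.
- **That every multi-day PD assessment is dated late.** This requires a qualifying PD finding on a scan before the last one.
- **That a later PET would delay the date.** The rule refers to radiographs for CT endpoints, and Protocol Table 9 labels PET response as metabolic and CT response as radiologic, so this is doubtful.
- **That the typical delay is 14/3 = 4.7 days.** That figure needs two scans placed at random over 14 days with PD always on the first. If PD were equally likely to appear first on either scan, it would halve to about 2.3 days, before allowing for the unknown share of multi-day series. The documents support none of these assumptions.

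**Conclusion.** The point holds for investigator-assessed progression. Where an earlier radiograph in a multi-day series already meets a PD criterion, SAP 4.1.2.5 dates PD late, and investigator PFS is longer by the gap to the last scan. The ceiling of 14 days (0.46 months) per affected event assumes that the CT window means 7 days either side. The average effect cannot be stated, because the documents do not give the frequency of multi-day series or of early PD findings within them. The effect is descriptive and touches secondary endpoints only. The primary IRC-assessed ORR and its 84.5% power do not change. This is a cheap improvement to the wording of the plan and does not threaten its main conclusion.

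**What to change.** - In SAP 4.1.2.5, date investigator PD at the earliest radiograph in the series that meets a PD criterion.
- Keep the last-radiograph date for first CR or PR and for censoring.
- Word SAP Table 1 so that PD at scheduled and unscheduled assessments follows the same rule.
- Check which convention section 10.1 of the Independent Review Charter uses, so that IRC and investigator dates can be compared.

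The cost is a few lines of SAP text and minor programming. Finding the last radiograph already requires the individual scan dates, so little new data should be needed. Investigator PFS may come out a few days shorter. If the charter dates IRC progression at the last scan, IRC and investigator dates would then follow different rules, and that mismatch should be noted when the two are compared.

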6.9.3 Disease assessment

If an unscheduled assessment is performed and the patient has not progressed, every attempt should be made to perform the subsequent assessments at their scheduled visits.

In the event disease progression is suspected due to physical examination or laboratory test, a CT and/or PET scan must be performed to confirm disease progression. If medically appropriate, it is recommended that uncertain disease progression should be confirmed by an alternative diagnostic imaging modality or biopsy, e.g. diagnostic quality CT/biopsy to confirm metabolic disease progression, or cytologic test to confirm malignant effusion. If the investigator is in doubt as to whether progression has occurred, it is advisable to continue treatment until the next scheduled assessment or sooner if clinically indicated and reassess the patient's status. If repeated scans confirm progression, then the date of the initial scan should be declared as the date of progression.

It is important to follow the assessment schedule as closely as possible. Please refer to the study plan (Table 2 and Table 3).

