Patients who have signs and symptoms of progression outside of the scheduled assessment should be evaluated by the investigator with a physical exam and laboratory assessments to determine if disease progression is present. In the event disease progression is suspected due to physical examination or laboratory test, a CT and/or PET scan must be performed to confirm disease progression. If medically appropriate, it is recommended that uncertain disease progression should be confirmed by an alternative diagnostic imaging modality or biopsy, e.g. diagnostic quality CT/biopsy to confirm metabolic disease progression, or cytologic test to confirm malignant effusion.

The presence of residual symptoms in the absence of detectable disease by imaging does not preclude the designation CR. In the context of an agent associated with a flare reaction, caution must be exercised not to confuse the possible tumor flare with progressive disease. It is recommended that either a biopsy be performed or the lesion be reassessed in at least 2 weeks, and if there is continued evidence of tumor progression, the date of progressive disease is the previous evaluation.

5. References

Cheson BD et al. 2014

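### The SAP's programmed investigator progression date omits the protocol's back-dating of doubtful progression, so an affected patient's investigator PFS and DoR can end one scan gap late

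*SAP*

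**What the plan says.** **SAP.** Section 4.1 names the source for investigator endpoints: "Investigator (local radiology) overall responses at each assessment/time point. Participant overall response date will be derived by program". Section 4.1.2.5 gives the rule: "The CT date of progression is defined as the radiographic assessment date of the first time point with overall response as PD". An investigator-declared progression date is not listed as a source. Neither section, nor the PFS censoring scheme in Table 1, contains a back-dating step.

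**Protocol.** Section 6.9.3 covers the investigator who is unsure whether progression has occurred: "it is advisable to continue treatment until the next scheduled assessment or sooner if clinically indicated", and then "If repeated scans confirm progression, then the date of the initial scan should be declared as the date of progression". Appendix VI section 4, on possible tumor flare, asks for a biopsy or a reassessment after at least two weeks and adds: "if there is continued evidence of tumor progression, the date of progressive disease is the previous evaluation".

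**Endpoints concerned.** SAP 4.1.2.5 makes investigator-assessed PFS and DoR secondary endpoints. SAP 4.1.2.1 ties the end of response to the PFS progression date, so a shift in one is a shift in both.

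**The concern.** The two documents can give different progression dates for the same patient. The protocol goes back to the scan that first raised the doubt. The program goes to the earliest assessment carrying PD. These agree only if the doubtful scan itself carries PD in the database.

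That is not assured. Appendix VI requires PD, SD, PR or CR at every assessment and has no equivocal category. An investigator who doubts progression and arranges another scan could reasonably enter a non-PD response. If that entry stays, the program passes over it and takes the confirming scan, and the patient's PFS and DoR are longer than the protocol's rule would make them.

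SAP 4.1 sends the reader to protocol section 6.9 and Appendix VI for the response criteria. Those are the places that hold the back-dating rules, so the omission does not read as a deliberate departure. SAP 5.5.3 plans no sensitivity analysis that might show the effect.

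**Working it through.** **Inputs**
- Cycle length: 21 days (SAP 2.2).
- CT within 7 days of Day 1 of Cycles 3, 6 and 9, then every 3 cycles (Protocol 6.9.1).
- Flare reassessment: 14 days or more (Protocol Appendix VI section 4).
- Months = days / 30.4375 (SAP 4.1.2).

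**1. The plan's own schedule figure.** Day 1 of Cycle c falls on study day 21 × (c − 1) + 1, so Cycles 3, 6, 9 and 12 start on days 43, 106, 169 and 232. Cycle 6 Day 1 is 105 days after first dose; 105 + 7 = 112 days, which is the two-visit limit in SAP Table 1. The schedule reproduces.

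**2. Size of one scan gap**

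| Case | Days | Months |
|---|---|---|
| Nominal: 3 × 21 | 63 | 2.07 |
| Window extremes, long: 63 + 7 + 7 | 77 | 2.53 |
| Window extremes, short: 63 − 7 − 7 | 49 | 1.61 |
| Early repeat at the flare minimum | 14 | 0.46 |
| Initial scan coded or re-coded PD | 0 | 0 |

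**3. One affected patient.** Suppose PR on day 43, a doubtful scan on day 106 recorded as SD, and PD on day 169.
- PFS under the SAP: 169 / 30.4375 = 5.55 months. Under Protocol 6.9.3: 106 / 30.4375 = 3.48 months.
- DoR under the SAP: (169 − 43 + 1) / 30.4375 = 4.17 months. Under the protocol: (106 − 43 + 1) / 30.4375 = 2.10 months.
- Both differ by 63 days, or 2.07 months. If the site amends day 106 to PD, the SAP rule returns day 106 and the difference disappears.

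**4. Cohort effect (illustration only).** The documents do not give the share of investigator progressions that are first doubtful, then confirmed, and left coded non-PD. Call it q. The mean shift among patients who progress is q × gap.

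| q (assumed) | 63-day gap | 14-day gap |
|---|---|---|
| 10% | 0.21 months | 0.05 months |
| 20% | 0.41 months | 0.09 months |
| 30% | 0.62 months | 0.14 months |

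The SAP reports Kaplan-Meier quartiles and rates, so these means show scale only; they do not predict the reported median.

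**5. What does not move.** The primary test uses IRC response. Its stated power of 84.5% reproduces as 84.48% (100 patients, 15% against 27%, reject at 23 or more responders) and involves no investigator progression date. Under SAP 4.1, IRC PFS and DoR use the progression date that the IRC reports.

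**The case against.** The strongest reply is that the SAP rule can already yield the protocol date. The protocol tells the investigator to declare the initial scan date. If the site carries that out by entering or amending the scan as PD, the earliest PD assessment is the initial scan. Nothing supplied says that a doubtful scan stays non-PD. The case report form and section 10.1 of the Independent Review Charter, to which SAP 4.1.2.5 refers for assessment dates, are not available. The SAP was also written against protocol version 5.0, while the protocol supplied is version 6.0, so whether the texts conflicted at the time cannot be checked. All of this stands, and it makes the shift conditional. It does not supply the missing rule.

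Three stronger readings are tempting, and the documents do not support them:
- **That investigator PFS and DoR as a whole are overstated by a scan interval.** Only an unknown subset of patients can be affected. Nor is 63 days a cap or an average: an early repeat gives less, and wide windows or doubt over two successive scans give more.
- **That the error can only run late.** It runs late in the situation described. But the SAP rule needs no confirmation, so a doubtful scan entered as PD and later not confirmed would be dated early.
- **That it creates false disagreement with the IRC.** The concordance analysis specified in Protocol 7.5.1 concerns ORR. Protocol 6.9.4.2 mentions a comparison only in general terms, and the legible SAP text plans none for PFS or DoR dates.

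The Appendix VI rule is also limited to agents associated with flare, and nothing supplied says that AZD4205 is one. Protocol 6.9.3 carries the point by itself.

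**Conclusion.** The point holds as a conditional inconsistency between the two documents. For a patient whose doubtful scan is recorded as non-PD, later confirmed as progression and not re-coded, the SAP dates investigator PFS and DoR one scan gap later than Protocol 6.9.3: nominally 63 days (2.07 months), about 14 days for an early repeat, and up to 77 days with visit windows. For everyone else whose progression date follows these rules, including patients whose initial scan is coded or re-coded PD, the shift is zero.

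The number of patients affected cannot be derived from the documents, so no cohort-level bias is demonstrated. The exposure is confined to two investigator-assessed secondary endpoints. It should be corrected because the correction is cheap and leaves a single dating rule, but it does not threaten the primary conclusion.

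**What to change.** Add one sentence to SAP 4.1.2.5: when a doubtful progression is confirmed by the repeat assessment, the initial time point is treated as PD and its scan date is the progression date; otherwise the earliest time point with PD is used. Put it into effect by re-coding the initial time point through a data query before database lock, so that the program keeps one rule and one data source and no separately declared date competes with it. Report the number of patients whose date changes.

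The cost is one SAP sentence and a data query. Investigator PFS and DoR may come out slightly shorter. The change concerns dating only and leaves the protocol's treatment guidance as it is.
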